1.2. Study Scheme

Figure 1: Study Scheme – Main Study – Double-blind Placebo-controlled

[figure not shown]
Abbreviations: twice daily (bid); Baseline (BL); End of Study (EoS); Early Termination (ET); once daily (QD); Visit (V); Virtual Visit (VV); Week (W); Total Daily Dose (TDD).

* For each participant, the last treatment visit will be the EoS at either Week 65 or Week 78 if the participant completes all study visits; or Early Termination (ET) visit if the participant withdraws from the study before Week 65.

Prilenia Therapeutics

Study drug: Pridopidine
Protocol Number: PL101-HD301

Figure 2: Study Scheme – Open-label Extension

* for the last participant(s) who is randomized to the Main study, the End of Study for the Main study will be V7/Wk 65.

Abbreviations: End of Study (EoS); EarlyTermination (ET); Open-label Extension (OLE); Visit (V); Week (Wk).

1.3. Schedule of Activities (SoA)

1.3.1. Schedule of Activities – Main Study – Double-blind, Placebo-Controlled

General note: every clinic visit, except Screening V1, Baseline V2, and V7 can be converted to virtual visits (VV) (e.g., via telephone). Refer to Appendix 10 (Section 10.10) for guidance.

Table 2: Schedule of Activities – Main Study – Double-blind, Placebo-Controlled

Study Period Procedures and Assessments	Screening ^a		Double-blind Titration Period	Double-blind, Placebo-controlled, Full-dose Maintenance Treatment Period												Double-blind Variable Period ^b	Follow-up Safety Assessment ^c	
Study Clinic Visit	V1		V2 BL ^d		V3			V4		V5		V6		V7 ^e		V8 (Main Study EoS ^{e,f} /ET ^g)	F/U	
Virtual Visit (VV)		VV1 BL			VV 2			VV3			VV 4							
Telephone Call Safety Visit				📞		📞		📞		📞		📞		📞		📞		
Study Week			Day1	2	4	8	13	19	26	32	39	45	52	58	65	72	78	80 (2 weeks after Main Study EoS/ET)
Visit Windows (days)	< 42	<7		±5	±5	±14	±14	±14 ^h	±14	±14 ^h	±14	±14 ^h	±14	±14 ^h	±14	±14 ^h	±5	
Informed consent	X (Main Study)													X (OLE)		X (OLE) if not obtained at V7		
Check willingness to enter OLE														X ⁱ				
Demography	X																	
Medical and psychiatric history (including smoking)	X																	
Prior medication and treatment history	X																	
Inclusion and exclusion criteria	X ^j																	

Prilenia Therapeutics

Study drug: Pridopidine
Protocol Number: PL101-HD301

Study Period Procedures and Assessments	Screening ^a		Double-blind Titration Period	Double-blind, Placebo-controlled, Full-dose Maintenance Treatment Period												Double-blind Variable Period ^b	Follow-up Safety Assessment ^c	
Study Clinic Visit	V1		V2 BL ^d		V3				V4		V5		V6		V7 ^e		V8 (Main Study EoS ^{e,f} /ET ^g)	F/U
Virtual Visit (VV)		VV1 BL			VV 2			VV3			VV 4							
Telephone Call Safety Visit				📞		📞		📞			📞				📞		📞	
Study Week			Day1	2	4	8	13	19	26	32	39	45	52	58	65	72	78	80 (2 weeks after Main Study EoS/ET)
Visit Windows (days)	<42	<7			±5	±5	±14	±14	±14 ^h	±14	±14 ^h	±14	±14 ^h	±14	±14 ^h	±14	±14 ^h	±5
Clinical lab tests (serum chemistry, hematology and urinalysis) ^k	X		X		X				X		X		X		X		X	
Pregnancy test (for WC/CBP) ^l	Serum		Urine (U)		U				U		U		U		U		U	
				Monthly urine pregnancy tests (at home)														
Full physical and neurological examination	X		X										X		X		X	
Brief physical examination					X				X		X							
12 lead ECG	X ^m		X ^{n,o}		X ^o				X ^p					X ^p		X ^{p,q}		
Vital signs ^r	X		X		X				X		X		X		X		X	
C-SSRS (Baseline version)	X																	
C-SSRS (since last visit version)			X		X	X	X	X	X	X	X	X	X	X	X	X	X	
UHDRS-TFC	X	X	X						X	X	X		X	X	X		X	
UHDRS-TMS	X		X						X		X		X		X		X	
UHDRS-IS	X																	

CONFIDENTIAL

Prilenia Therapeutics

Study drug: Pridopidine
Protocol Number: PL101-HD301

Study Period Procedures and Assessments	Screening ^a		Double-blind Titration Period	Double-blind, Placebo-controlled, Full-dose Maintenance Treatment Period												Double-blind Variable Period ^b	Follow-up Safety Assessment ^c	
Study Clinic Visit	V1		V2 BL ^d		V3				V4		V5		V6		V7 ^e		V8 (Main Study EoS ^{e,f} /ET ^g)	F/U
Virtual Visit (VV)		VV1 BL			VV 2			VV3			VV 4							
Telephone Call Safety Visit				📞		📞		📞		📞		📞		📞		📞	📞	
Study Week			Day1	2	4	8	13	19	26	32	39	45	52	58	65	72	78	80 (2 weeks after Main Study EoS/ET)
Visit Windows (days)	< 42	< 7			±5	±5	±14	±14	±14 ^h	±14	±5							
SDMT				X						X		X		X		X		
SWR				X						X		X		X		X		
Q-Motor	X ^g		X						X			X		X		X		
PBA-S (Short Form)		X	X			X		X			X	X	X			X		
CGI-S (modified)		X	X															
CGI-C								X		X		X		X		X		
HDQoL-P			X						X			X		X		X		
Benzodiazepines and antidepressants inquiry ^t	X	X	X	X	X	X	X	X	X	X	X	X	X	X	X	X	X	
Alcohol/illicit drug use inquiry	X	X	X	X	X	X	X	X	X	X	X	X	X	X	X	X	X	
Review of tolerability to study drug prior to dose escalation				X														
Randomization			X															
Dispense/collect study drug			X (dispense only)		X			X		X		X		X		X		
Review study compliance and adherence				X	X	X	X	X	X	X	X	X	X	X	X	X		

Prilenia Therapeutics

Study drug: Pridopidine
Protocol Number: PL101-HD301

Study Period Procedures and Assessments	Screening ^a		Double-blind Titration Period	Double-blind, Placebo-controlled, Full-dose Maintenance Treatment Period												Double-blind Variable Period ^b	Follow-up Safety Assessment ^c	
Study Clinic Visit	V1		V2 BL ^d		V3				V4		V5		V6		V7 ^e		V8 (Main Study EoS ^{e,f} /ET ^g)	F/U
Virtual Visit (VV)		VV1 BL			VV 2			VV3			VV 4							
Telephone Call Safety Visit				📞		📞		📞			📞		📞		📞		📞	
Study Week			Day1	2	4	8	13	19	26	32	39	45	52	58	65	72	78	80 (2 weeks after Main Study EoS/ET)
Visit Windows (days)	<42	<7		±5	±5	±14	±14	±14 ^b	±14	±14 ^b	±14	±14 ^b	±14	±14 ^b	±14	±14 ^b	±5	
Study drug administration				<===== X =====>														
Adverse event inquiry	X	X	X	X	X	X	X	X	X	X	X	X	X	X	X	X	X	
Concomitant medication inquiry	X	X	X	X	X	X	X	X	X	X	X	X	X	X	X	X	X	
Blood samples for PK analysis ^u									X				X		X		X	
Plasma sample for biomarkers analysis ^v	X ^w		X ^w						X				X		X		X	
Blood sample for genetic analysis ^{v,x}	X ^w		X ^w															
Blood sample for CAG repeat analysis ^{v,y}	X																	

Abbreviations: Baseline (BL); cytosine-adenosine-guanine (CAG); Clinical Global Impression of Change (CGI-C); Clinical Global Impression of Severity (CGI-S); Columbia-Suicide Severity Rating Scale (C-SSRS); electrocardiogram (ECG); End of Study (EoS); Early Termination (ET); Follow-Up (F/U); Huntington Disease Quality of Life Questionnaire-Participant (HDQoL-P); Independence Scale (IS); Problem Behaviors Assessment – Short Form (PBA-s); pharmacokinetic (PK); Quantitative motor (Q-Motor); Symbol Digit Modalities Test (SDMT); Stroop Word Reading (SWR); Total Functional Capacity (TFC); Total Motor Score (TMS); Unified Huntington Disease Rating Scale (UHDRS); Visit (V); Virtual Visit (VV); women of childbearing potential (WOCBP).

Table Footnotes:

a. A participant not meeting all eligibility requirements may be rescreened only once. Screening assessments may be repeated during the screening period if approved and at the discretion of the study Medical Monitor (or designee). After the screening period all screening assessments must be repeated except for Cytosine Adenine Guanine (CAG) repeat (provided the results are available from a prior screening period).

Prilenia Therapeutics

Study drug: Pridopidine
Protocol Number: PL101-HD301

- b. This period is variable in duration up to 13 weeks. Participants will continue to receive treatment during the double-blind variable period until they reach Week 78 or until the last participant randomized completes 65 weeks of treatment (2 weeks titration + 63 weeks full-dose), whichever comes first. As soon as the last participant reaches Week 65, the Main Study EoS visit for all remaining participants who are 4 weeks beyond their respective Week 65 visit needs to be conducted within 4 weeks.
- c. Follow-up visit in Main Study is only applicable to participants who are not continuing to Open-label Extension.
- d. All Baseline assessments should be done pre-dose, except post-dose ECG.
- e. For the last group of participants whose Week 65 visit is within 4 weeks of last participant's Week 65 visit in the Main Study, the End of Study visit will be V7.
- f. After completing the Main Study EoS visit, eligible participants will have the option to continue for an Open-label Extension.
- g. When a participant discontinues study drug but continues to be followed in the study, they should first do ET visit and then continue with the follow-up off study treatment as scheduled.
- h. Visit window can be expanded any post Week 4 (V3) in-clinic visit window to ± 28 days; this applies to V4-8). The expansion of the in-clinic visit window is only in case of a global pandemic.
- i. To be done once, as early as Main Study Week 58, or at V7 (Main Study Week 65)/Main Study Week 72 (depending on when the participant is anticipated to transition to OLE).
- j. Inclusion/exclusion criteria should be met before Baseline visit.
- k. Safety laboratories should not be collected for participants who are off drug and remain in the study, unless there are abnormalities requiring follow-up.
- l. Serum pregnancy test will be performed at Screening. At Baseline visit, urine pregnancy test will be performed before first dose. Both test results must be known before first dosing. Urine pregnancy test will be performed at subsequent timepoints. An indeterminate or positive reading for the urine pregnancy test should be followed-up by a serum pregnancy test and the participant should be referred to a gynecologist if required. During the Treatment period, urine pregnancy tests will be performed monthly. Refer to Appendix 4 Section 10.4.
- m. Single ECG to assess eligibility.
- n. Baseline pre-dose assessment will include triplicate ECG administrations.
- o. Single ECG 1-2 hours post-dose.
- p. Single ECG pre-dose.
- q. Only for participants not continuing to Open-label Extension (single ECG). Participants continuing to OLE, will have triplicate ECG (pre-dose) at V8.
- r. Vital signs (body temperature, systolic and diastolic blood pressure, and heart rate) will be measured in a supine position after 5 minutes rest; thereafter, blood pressure should be measured again after standing for 2 minutes.
- s. For training purposes only.
- t. This information will be collected as part of the concomitant medication inquiry.
- u. Blood samples for plasma concentration of study drug will be collected 1-2 hours **after** dosing and **after** the ECG. PK samples should not be collected from participants who are off drug and remain in the study.
- v. Always collect blood after ECG is administered (not before).
- w. Sample analysis will be drawn at Screening **or** Baseline.
- x. Sampling analyses for DNA extraction will be performed only once during the study, at Screening or at Baseline, for future genetic analysis related to pridopidine response or HD.
- y. Sampling analyses for CAG, only if needed.

1.3.2. Schedule of Activities – Open-label Extension (OLE)

Table 3: Schedule of Activities – Open-label Extension

Study Period Procedures and assessments	Open-Label Titration Period		Open-Label Full-dose Treatment Period					Followup Safety Assessment	
	OLE V1 ^a (same as Main Study V8)		OLE V2		OLE V3		OLE V4+ ^b	OLE EoS /ET ^b	OLEF/U
Study Clinic Visit									
Telephone Call Safety Visit		📞		📞		📞			📞
OLE Study Week	OLE Day 1 (same as Main Study Wk 78/EoS)	OLE Wk 2	OLE Wk 4	OLE Wk 13	OLE Wk 26	OLE Wk 39 & every 26 wks thereafter	OLE Wk 52 & every 26 wks thereafter	X	+2 weeks after OLE EoS/ET
Visit Windows (days)		±1	±5	±5	±14	±14	±14	±14	±5
OLE Informed consent	X (if not obtained at Main Study V7)								
Re-confirm eligibility to OLE	X								
Clinical laboratory tests (serum chemistry, hematology) ^d	X		X		X		X	X	
Urinalysis ^e	X								
Pregnancy test (for WOCBP)	U		U		U		U	U	
	Monthly urine pregnancy test (at home)								
Brief physical examination	X (full PE)		X		X		X	X	
12 lead ECG	X ^{f,g}		X ^g		X ^h			X ^h	
Vital signs	X		X		X		X	X	
C-SSRS (since last visit version)	X		X	X	X	X	X	X	X
UHDRS-IFC	X				X		X	X	
UHDRS-TMS	X				X		X	X	
SDMT	X				X		X	X	
SWR	X				X		X	X	
Motor	X		X		X		X	X	
PBA-S (Short Form)	X		X		X	X	X	X	X
CGI-C	X				X		X	X	
HDQoL	X				X		X	X	

Prilenia Therapeutics

Study drug: Pridopidine
Protocol Number: PL101-HD301

Study Period Procedures and assessments	Open-Label Titration Period		Open-Label Full-dose Treatment Period					Follow-up Safety Assessment	
	OLE V1 ^a (same as Main Study V8)		OLEV2		OLE V3		OLEV4+ ^b	OLE EoS /ET ^b	OLEF/U
Study Clinic Visit									
Telephone Call Safety Visit		📞		📞		📞			📞
OLE Study Week	OLE Day 1 (same as Main Study Wk 78/EoS)	OLE Wk 2	OLE Wk 4	OLE Wk 13	OLE Wk 26	OLE Wk 39 & every 26 wks thereafter	OLE Wk 52 & every 26 wks thereafter	X	+2 weeks after OLE EoS/ET
Visit Windows (days)		±1	±5	±5	±14	±14	±14	±14	±5
Benzodiazepines and antidepressants inquiry	X	X	X	X	X	X	X	X	X
Alcohol/illicit drug use inquiry	X	X	X	X	X	X	X	X	X
Dispense/collect study drug	X		X		X		X	X (collect only)	
Review study compliance and adherence	X	X	X	X	X	X	X	X	X
Study drug administration	<=====X=====>								
Adverse event inquiry	X	X	X	X	X	X	X	X	X
Concomitant medication inquiry	X	X	X	X	X	X	X	X	X
Plasma sample for biomarkers analysis					X ^c		X	X ^c	

Abbreviations: Clinical Global Impression of Change (CGI-C); Columbia-Suicide Severity Rating Scale (C-SSRS); electrocardiogram (ECG); End of Study (EoS); Early Termination (ET); Follow-up (F/U); Huntington Disease Quality of Life Questionnaire (HDQoL); Open-label Extension (OLE); Physical Examination (PE); Problem Behaviors Assessment—Short Form (PBA-s); Symbol Digit Modalities Test (SDMT); Stroop Word Reading (SWR); Total Functional Capacity (TFC); Total Motor Score (TMS); Unified Huntington Disease Rating Scale (UHDRS); Visit (V); women of childbearing potential (W●CBP).

Table Footnotes:

[figure not shown]
[figure not shown]
- The OLE VI is the same as Main Study V8 (or V7/W65 for the last group of participants in the Main Study). Assessments do not need to be repeated if conducted as part of the Main Study.
- A participant who discontinues study drug at any point during the OLE, must also be withdrawn from the study and attend an EoS visit.
- In-clinic visit window can be expanded to ±28 days; this applies to all in-clinic visits including OLE V1-4+ and OLE F/U. The expansion of the in-clinic visit window is only in case of a global pandemic.
- Collect blood after ECG is administered (not before).
- Urinalysis will be done as part of Main Study V8, not as part of OLE
- Triple ECG pre-dose.
- Single ECG 1-2 hours post-dose.
- Single ECG pre-dose.

2. INTRODUCTION

2.1. Study Rationale

Huntington Disease (HD) is an autosomal dominant, progressive fatal neurodegenerative disorder characterized by motor, cognitive, and behavioral abnormalities. While medications to treat chorea and some behavioral symptoms are available, no therapy has yet proven able to modify the progressive and inexorable functional decline of the disease. A therapy that maintains functional capacity and prevents or delays the development of disability represents a critically unmet clinical need.

Pridopidine, a novel small molecule under development for the treatment of HD has high affinity

Prilenia Therapeutics

Study drug: Pridopidine
Protocol Number: PL101-HD301

Prilenia Therapeutics

Study drug: Pridopidine
Protocol Number: PL101-HD301

Prilenia Therapeutics

Study drug: Pridopidine
Protocol Number: PL101-HD301

The purpose of this Phase 3 study is to further evaluate the effect of pridopidine 45 mg bid on functional capacity, as well as motor and behavioral features of HD in early-stage participants (TFC 7-13).

2.2. Background

HD is a fatal neurodegenerative disorder characterized by progressive deterioration of motor and cognitive functions, as well as behavioral and psychiatric disturbances. The disease has an autosomal dominant inheritance and is caused by an expanded cytosine-adenine-guanine (CAG) repeat in the huntingtin gene (HTT) on chromosome 4, encoding the mutant protein huntingtin (Huntington's Disease Collaborative Research Group, 1993).

The estimated prevalence of HD in North America, North-Western Europe, and Australia ranges from 5.96 to 13.7 cases per 100,000 people (Fisher, 2014; Rawlins, 2016). The age of onset of the signs and symptoms of HD and the rate of disease progression can vary greatly. Adult-onset HD most often begins between 30 and 40 years of age. The illness generally lasts 15 to 20 years and is fatal. Following diagnosis, motor and cognitive functions steadily decline, ultimately leading to a state of immobility, dementia, and premature death (Ross, 2014).

In HD to date, only 2 drugs, tetrabenazine and deutetrabenazine, have been approved for the management of chorea. A number of medications are used off-label to control motor and psychiatric symptoms arising from HD.

A detailed description of the chemistry, pharmacology, efficacy, and safety of pridopidine is provided in the Investigator's Brochure (IB).

2.3. Benefit/Risk Assessment

More detailed information about the known and expected benefits and risks and reasonably expected AEs of pridopidine may be found in the IB.

2.3.1. Risk Assessment

Potential Risk of Clinical Significance	Summary of Data/Rationale for Risk	Mitigation Strategy
Study drug Pridopidine		
QT Prolongation	
Known risk identified in pre-clinical and clinical studies as a result of I_{Kr} potassium channel block in ventricular myocardium. Excessive QT prolongation is a recognized surrogate marker for a specific type of ventricular tachycardia, Torsade de Pointes. Exposure-response modeling based on dosing of pridopidine up to 112.5 mg bid suggests a linear response of QTcF to increasing drug exposure (refer to Appendix 9 Section 10.9). At 45 mg bid, the dose evaluated in this trial, the estimated QTcF prolongation is 6.6 ms and not considered clinically meaningful.
	
Participants will be excluded if they have a clinically significant heart disease, a clinically significant history of arrhythmia, symptomatic or uncontrolled atrial fibrillation despite treatment, or asymptomatic sustained ventricular tachycardia, or presence of left bundle branch block.
 
Participants with known history of congenital long QT syndrome or a first degree relative with this condition will be excluded.
 
Participants with clinically significant bradycardia, sick sinus syndrome, complete atrioventricular block, congestive heart failure, polymorphic ventricular tachycardia, clinically relevant hypocalcemia, hypokalemia or hypomagnesemia will be excluded.
 
ECG parameters will be closely monitored throughout the study (refer to Appendix 8, Section 10.8).
 
Participants will be required to discontinue study drug during the study if they have symptomatic or uncontrolled atrial fibrillation, confirmed ventricular tachycardia, presence of left bundle branch block

Decreased creatinine renal clearance	
Identified risk in clinical studies. There have been no serious outcomes relating to the decrease, and discontinuation of the pridopidine treatment results
	
Participants with a creatinine clearance (CrCl) <30 mL/min will be excluded.
 
Creatinine values will be monitored throughout the study.

Potential Risk of Clinical Significance	Summary of Data/Rationale for Risk	Mitigation Strategy
	in the return of creatinine to normal values.	Participants will be discontinued from the study if their CrCl reaches <30 mL/min during the study.

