7.1.2. Creatinine Clearance Stopping Rules

Participants with CrCl <30 mL/min, calculated using the Cockcroft-Gault equation $[(140 - \text{age}) \times \text{mass (kg)} \times [0.85 \text{ if female}] / 72 \times \text{serum creatinine (mg/dL)}]$, at any timepoint after the Baseline visit 2 will be requested to return to the clinic for an unscheduled visit 1 week later, to repeat the CrCl test one more time for confirmation. If the repeated CrCl value is confirmed to be <30 mL/min, the participant will be discontinued from the study drug.

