7.2. Discontinuation of Study Drug

In rare instances, it may be necessary for a participant to permanently discontinue (definitive discontinuation) study drug. A participant may discontinue study drug for reasons including but not limited to:

- AE
- Death
- Lost to follow-up
- Non-compliance with study drug
- Physician decision
- Pregnancy
- Protocol deviation
- Study terminated by Sponsor
- Withdrawal of consent by participant
- Loss of capability to consent

The reason for participant discontinuation from the study drug will be recorded in the eCRF.

Participants who are **discontinued from study drug** during the Main Study will be encouraged to continue their participation in the study and perform all the scheduled visits and assessments, while off study drug. If participants are unable/unwilling to attend in-clinic visits, these visits can be replaced with virtual phone visits except for the following: Main Study Week 65, Week 78/EoS and ET visits. If a clinic visit is replaced by a virtual visit at Week 4, Week 26, Week 39, and Week 52, the UHDRS-TFC, clinical laboratories, and vital signs should not be assessed (refer to Appendix 10, Section 10.10). They will continue to be closely monitored by the Investigator and will be referred for psychiatric evaluation per the Investigator's medical judgment. Participants who are discontinued from study drug during the OLE will be withdrawn from the study and will be requested to return to an EoS visit.

See the SoA (Table 2 – Main Study, and Table 3 – OLE) for data to be collected at the time of study drug discontinuation and follow-up and for any further evaluations that need to be completed.

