7.3. Participant Withdrawal from the Study

A participant may withdraw from the study at any time at his/her own request or may be discontinued by the Investigator. Participants may be withdrawn from the study for any of the following reasons:

- Death
- Withdrawal by participant
- Lost to follow-up
- Study terminated by Sponsor

The reason for participant withdrawal from the study will be recorded on the eCRF. At the time of withdrawal, ET visit procedures outlined in the SoA ([Table 2 – Main Study](#), and [Table 3 – OLE](#)) should be completed, if possible.

If the participant withdraws consent for disclosure of future information, the Sponsor may retain and continue to use any data collected, based on local regulations, before such a withdrawal of consent. Participants withdrawing consent may request destruction of any samples taken and not tested, and the Investigator must document this request and proof of destruction in the site study records.

If a participant withdraws from the study, he/she may request the destruction of any samples taken and not tested, and the Investigator must document this in the site study records.

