3. Compound symmetry with heterogeneous variances (CSH),
4. Toeplitz (TOEP),
5. Autoregressive (1) [AR(1)], and
6. Compound Symmetry (CS).

Denominator degrees of freedom for the F-test for fixed effects will be estimated using the Kenward-Roger approximation. The least square mean (LSM) and standard error (SE) of the LSM for each treatment group, the 95% CI and p-value for the comparisons (change from Baseline in pridopidine 45 mg bid vs. placebo) will be presented at Week 65.

For EMA regions, the main estimand is defined as **EMA-Estimand**:

- Treatment: Pridopidine 45 mg bid or placebo (on background of standard of care) that participants are randomized to
- Population: Early HD Participants (HDI & HD2) defined through the study inclusion/exclusion criteria. The ITT population will be used in analyzing this estimand
- Variable: Change from Baseline to Week 65 in UHDRS-TFC
- Population Level Summary: LS-Mean difference between pridopidine 45 mg bid and placebo from MMRM model in change of UHDRS-TFC from Baseline to Week 65
- ICEs and Strategies for Addressing ICEs:

ICEs include treatment discontinuation or death and will be handled by a composite of treatment policy and hypothetical strategies.

- Treatment policy strategy will apply to all observed values including those collected after treatment discontinuation as these values reflect the remaining off-drug treatment effect in reality.
- Hypothetical strategy will apply to missing values after the last observed values. The method of MI will be applied to impute the missing data using PMM with control-based pattern imputation under MNAR assumptions (details in Section 5.8.1).

Since UHDRS-TFC is used as a continuous variable in the MI procedure, the imputed values will take continuous values instead of the discrete values ranging from 0 to 13. To avoid the influence of extreme values outside the range, the continuous values will be categorized to 0 if the imputed values < 0.5 , and to 13 if the imputed values ≥ 12.5 . All the other values in $[0.5, 12.5)$ will be rounded to the nearest integer between 1 and 12.

The MI method uses SAS PROC MI and MIANALYZE to generate multiple complete datasets and combine the model results from them as described in Section 5.8.1. The LSM and associated SE for each treatment group, the 95% CI and p-value for the comparisons (pridopidine 45 mg bid vs. placebo) will be presented at Week 65.

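### For the Main Study, Protocol 2.3.1 takes a participant with creatinine clearance below 30 mL/min out of the study and mentions no confirmation, while 7.1.2 and 7.2 stop study drug after a confirmed repeat and keep follow-up

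*Protocol*

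**What the plan says.** The mitigation column of the risk table in Protocol 2.3.1 reads: "Participants will be discontinued from the study if their CrCl reaches <30 mL/min during the study". The sentence has no confirmation step and does not point to 7.1.2.

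Protocol 7.1.2 keeps the threshold but describes a different sequence. After a post-Baseline value below 30 mL/min the participant is asked to "return to the clinic for an unscheduled visit 1 week later, to repeat the CrCl test one more time for confirmation". Then: "If the repeated CrCl value is confirmed to be <30 mL/min, the participant will be discontinued from the study drug".

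Protocol 7.2 says that Main Study participants who stop drug "will be encouraged to continue their participation in the study and perform all the scheduled visits and assessments, while off study drug". For the OLE it says: "Participants who are discontinued from study drug during the OLE will be withdrawn from the study".

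Protocol 7.3 begins its list with "Participants may be withdrawn from the study for any of the following reasons" and gives four: death, the participant's own withdrawal, loss to follow-up and termination by the sponsor. CrCl is not among them.

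On the analysis side, SAP 7.2 says of the EMA estimand: "Treatment policy strategy will apply to all observed values including those collected after treatment discontinuation". The non-EMA estimand in the same section also uses every observed value, whether or not an intercurrent event has occurred.

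**The concern.** Leaving the study and stopping the drug are separate outcomes in this protocol, handled in 7.3 and 7.2 respectively. The plan relies on the difference, because both primary estimands need Total Functional Capacity (TFC) scores collected after drug has been stopped. In the Main Study, a site that follows 2.3.1 literally would end follow-up for a participant whom 7.1.2 and 7.2 would keep under observation off drug.

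If that happened before Week 65, TFC values that could have been observed would be missing. The EMA analysis would impute them from the placebo-based model, and the non-EMA MMRM would handle them under missing at random (SAP 5.8.1.2 and 7.2). Sites could also act differently on the same laboratory result, because one passage asks for a repeat test and the other does not mention one.

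**Working it through.** This is a comparison of text. The documents give no event rate, so no effect size can be computed.

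**1. The two rules side by side (Main Study).**

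| | Protocol 2.3.1 | Protocol 7.1.2 with 7.2 |
|---|---|---|
| Threshold | CrCl below 30 mL/min | CrCl below 30 mL/min |
| Confirmation | none mentioned | one repeat, a week later |
| Consequence | leaves the study | stops study drug |
| Follow-up afterwards | ends, with an ET visit if possible (7.3) | all scheduled visits encouraged, off drug |

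The threshold agrees. The consequence conflicts. On confirmation, one passage requires it and the other is silent.

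**2. Is 2.3.1 only using loose words?** The QT row of the same table says: "Participants will be required to discontinue study drug during the study if they have symptomatic or uncontrolled atrial fibrillation". The table therefore uses drug wording in one row and study wording in the next. Read at face value, the CrCl row means something different.

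**3. Which other text fits which rule?** Section 4.1 encourages participants who stop drug early to stay in the study. Footnote g of the Main Study schedule has them do an ET visit and then continue as scheduled. SAP 7.1.1 lists meeting the CrCl stopping rules as a cause of treatment discontinuation. These places fit 7.1.2, and none repeats the consequence in 2.3.1.

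**4. What a literal reading of 2.3.1 would cost one participant.** Inputs: laboratory visits at Weeks 4, 26, 39, 52, 65 and 78 (SAP 8.6); in-clinic TFC visits at Weeks 26, 39, 52, 65 and 78 (SAP 5.5.4); ET values assigned forward to a scheduled visit (SAP 5.5.3). Assumptions: the participant leaves soon after the low value, an in-clinic ET visit with TFC takes place, and SAP 5.5.3 means the next scheduled TFC visit. Missing visits up to Week 65 = TFC visits still due − 1 filled by the ET value.

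| Low value at | TFC visits still due up to Week 65 | Filled by ET value | Missing | Week 65 TFC |
|---|---|---|---|---|
| Week 4 | 26, 39, 52, 65 (4) | 26 | 4 − 1 = 3 | missing |
| Week 26 | 39, 52, 65 (3) | 39 | 3 − 1 = 2 | missing |
| Week 39 | 52, 65 (2) | 52 | 2 − 1 = 1 | missing |
| Week 52 | 65 (1) | 65 | 1 − 1 = 0 | ET value, taken early |
| Week 65 or 78 | none | not needed | 0 | due no later than the laboratory visit |

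Without an ET assessment, the first four rows lose 4, 3, 2 and 1 visits. Under 7.1.2 with 7.2 these visits remain planned, but attendance is only encouraged, so the Week 65 value is not assured there either.

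**5. OLE.** Section 7.2 withdraws OLE participants who stop drug, so leaving the study and stopping drug coincide. Only the difference on confirmation remains.

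**The case against.** The strongest reply is that 2.3.1 is a background summary of mitigation measures and 7.1.2 is the operative rule. The QT row of that table also leaves out the QTcF thresholds given in 7.1.1, so the table does not set out to restate the stopping rules in full. On this view silence about a repeat test is not a rival trigger, and the rest is one missing word.

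Much of this stands. Most operative text fits 7.1.2, and no analysis section relies on 2.3.1. But no text says that 7.1.2 takes precedence, and the consequence in 2.3.1 is stated, not omitted. The clause in the SAP Preface that the SAP prevails concerns differences between SAP and protocol, so it does not settle a conflict inside the protocol.

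A reader might infer more than the documents support:

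- *That 2.3.1 sets a first-value trigger.* It says nothing about a first value. It only lacks a confirmation step.
- *That the tolerability count and the responder flag are left open.* Both refer to the Stopping Rules (SAP 3.2.8 and 7.4.2). For CrCl, that term belongs to 7.1.2 and does not appear in the 2.3.1 sentence.
- *That every case loses its Week 65 value under one passage and keeps it under the other.* ET values can be carried to a scheduled visit, low values at Week 65 or later need cost nothing, and staying in the study off drug is voluntary.
- *That losses would fall mainly in the active arm.* Section 2.3.1 calls reduced clearance an identified risk, but the documents give no rate of values below 30 mL/min in either arm.

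**Conclusion.** The inconsistency is real and the sentence in 2.3.1 is wrong as written, in the sense that it cannot stand beside 7.1.2 and 7.2 for the Main Study. The consequence differs (study or study drug), and 2.3.1 does not mention the confirmation that 7.1.2 requires.

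The possible harm is loss of off-drug TFC values before Week 65 that both primary estimands are meant to use, and uneven handling across sites. It arises only if a site follows 2.3.1 literally. Its size cannot be stated because no event rate is given and ET values may replace part of the loss. No effect on the primary result is claimed. The point is minor and the conflict on consequence is limited to the Main Study.

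**What to change.** Revise the one sentence in Protocol 2.3.1 so that it agrees with 7.1.2 and 7.2 on two matters: whether the consequence is leaving the study or stopping study drug, and whether a confirmed repeat is needed. Add a cross-reference to 7.1.2 so that the rule is stated in full in one place. If the Main Study and the OLE are meant to differ in consequence, as 7.2 implies, the sentence should say which period it covers. Which clinical rule is right is for the sponsor and the investigators to settle.

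The cost is one protocol sentence. The SAP needs no change for the tolerability count or the responder flag.
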